9.2.3 Observation Period

Each patient will be followed from the date of first dose of cladribine tablets until loss to follow-up, withdrawal of consent, death, or the end of the data collection period, whichever comes first. Patients will be followed for 24 months from first dose and up to 30 months for those patients who may require a delay of initiation of Year 2 treatment for up to 6 months due to low lymphocyte counts. Follow-up will continue regardless of cladribine tablets discontinuation.

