Data analysis	
All patients starting treatment with cladribine tablets will be included in the analyses.
 
The primary endpoint will be analyzed at Month 24. All secondary endpoints on relapse rates, PROs, MRI, and treatment patterns will be analyzed at Month 12 (12-month interim analysis) and Month 24 (final analysis). PRO data will be analyzed once the first 30 patients reach the 6-month follow-up as well as at Month 6 for all enrolled patients. Safety data will also be assessed at Month 6 for the first 30 patients enrolled as well as at Months 12 and 24., for all patients, unless Year 2 treatment is delayed in which case the final safety assessment would occur at Month 30.
 
Descriptive statistics will be used to summarize data. If the outcome in question is a continuous variable, the number of observations, number of missing values, mean, standard deviation (SD), median, first quartile and third quartile, minimum and maximum values will be presented; if the outcome is categorical, numbers and percentages of patients for each of the categories and numbers and percentages of missing values will be presented.
 
Where appropriate, 95% CIs will be presented. For continuous data, CIs for the mean will be calculated assuming a normal distribution of the data. CIs for binary endpoints will be presented using the Clopper-Pearson method.
 
Time to event data will be analyzed both descriptively as continuous data and through Kaplan-Meier analysis.
 
The primary study outcome of ARR over the 24-month period will be accompanied by the respective 95% CI. Sensitivity analyses of the ARR will be performed considering the relapses as count data and using a negative binomial regression model with time as explanatory variables. A zero-inflated negative binomial regression model will also be considered.

Milestones	
First Patient First Visit (first patient to sign Informed Consent Form [ICF]): 31-July-2019
 
75 Patients Consented: 28 Feb 2020
 
150 Patients Consented: 30-Nov-2020
 
Last Patient First Visit (last patient to sign ICF): 28-Nov-2022
 
Last Patient Last Visit: 03-Jan-2025

Company substance code: 700568
Protocol number: MS700568_0079

	Database Lock: 17-Feb-2025
	Key Stats Available: 14-Jul-2025
	Clinical Study Report: 19-Sep-2025

Amendments and Updates

Amendment Number	Protocol Version	Date	Section of Study Protocol	Amendment or Update	Reason

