## 5 Objectives and Endpoints

Objectives	Endpoints (Outcome Measures)	Endpoints (Outcome Measures) Timeframe	IAP Section
Primary			
To estimate the annualized relapse rate (ARR) over a 24-month period in patients with Relapsing form of Multiple Sclerosis (RMS), including relapsing-remitting multiple sclerosis (RRMS) and active secondary progressive multiple sclerosis (aSPMS) who are treated with cladribine tablets in a real-world setting and after suboptimal response to any oral or infusion Disease-Modifying Drug (DMD) approved in the United States (US) for RMS	ARR over 24 months of treatment with cladribine tablets (prospectively collected data)	24-month period from first dose of cladribine tablets (or 30 months if Year 2 treatment is delayed)	Section 14.1
Secondary	
To assess Patient-Reported Outcomes (PROs), treatment adherence, and treatment satisfaction during treatment with cladribine tablets
 
Baseline scores, scores at the timepoints, and change in scores from Baseline to timepoints (Month 6, 12, and 24) for the following PROs (collected via electronic PRO [ePRO] at the practice or at the patient's home):
 

• 14-Item Treatment Satisfaction Questionnaire for Medication (TSQM)

• 36-Item Short Form Health Survey (SF-36)

• Modified Fatigue Impact Scale – 5-item version (MFIS-5)

• Beck-Depression Inventory – Fast Screen (BDI-FS) (7 items)

• Work Productivity Activity Impairment – Multiple Sclerosis (WPAI-MS) (6 items)

	24-month period from enrollment	Section 16.3 and Section 16.4

Objectives	Endpoints (Outcome Measures)	Endpoints (Outcome Measures) Timeframe	IAP Section
	
 
Patient Determined Disease Steps (PDDS) scale
 
 
Treatment adherence based on modified versions of the MS-TAQ; data to be collected via ePRO at Baseline (modified for once- or twice-daily oral dosing to assess adherence during last previous oral DMD treatment, or modified for infusion dosing to assess adherence to last previous infusion DMD treatment, only baseline scores) and at the end of Months 1, 2, 13, and 14 (modified for cladribine tablets, only scores at the different time points)
	Timepoints for TSQM, SF-36, MFIS-5, BDI-FS, WPAI-MS, and PDDS: Baseline, Months 6, 12, and 24 (or 30 months if Year 2 treatment is delayed) Adherence assessment timepoints: Baseline (adherence to previous DMD), Months 1, 2, 13, and 14 (adherence to cladribine)	

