### **6.5                    Final Analysis**

A final analysis will be performed on the 24-month data (or 30 months if Year 2 treatment is delayed) for all patients at the end of the study. The corresponding cutoff is expected by the end of March 2025.

The final analysis will include all the endpoint analyses related to the objectives of the study. For the PROs, the actual value at each visit and the change in scores from Baseline to Months 6, 12, and 24 will be considered. A comparison of the characteristics of patients who complete the study vs. those who drop out will be conducted as well.

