### Subgroups:

The following subgroups will be defined:

- Patients completing the 24-month study
- Patients not completing the 24-month study (i.e., lost to follow-up, withdrawing consent, protocol deviations)
- Patients not completing the treatment (i.e., completing Year 1 treatment but not Year 2 treatment, or not completing both courses of treatment each year)
- Type of MS at screening: RRMS, aSPMS, PPMS, CIS
- Patients diagnosed with MS <24 months before transitioning to cladribine tablets
- Centers
  - Pooling of centers: Because of the high number of participating centers and the anticipated small number of patients in each center, data will be pooled across centers,

and the factor centers will not be considered in statistical models or for subgroup analyses.

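### The 24-month relapse outcomes run to as much as 30 months when Year 2 is delayed, which raises the unannualized relapse proportions, and a shifted Visit 6 could fall after study closure

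*Protocol*

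**What the plan says.** **Follow-up.** Protocol 9.2.3 starts the clock at first dose. It stops it at loss to follow-up, withdrawal, death or the end of data collection, whichever is earliest. The planned length is 24 months, and "up to 30 months for those patients who may require a delay of initiation of Year 2 treatment for up to 6 months".

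**Outcome windows.** SAP Section 5 gives the primary ARR a "24-month period from first dose of cladribine tablets (or 30 months if Year 2 treatment is delayed", and gives the other relapse outcomes the same 24-or-30-month rule.

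- Primary ARR (SAP 14.1.1): relapses divided by days from first dose to study completion or discontinuation, times 365.25, with no upper limit on the days.
- Sensitivity ARR (SAP 14.1.1): time is bounded at 731.5 days, or at 366.25 days when relapse information exists for the first year only.
- 12-month ARR (SAP 14.2): time is limited to one year.
- Proportions with a relapse, a hospitalized relapse or a glucocorticoid-treated relapse (SAP 14.2): reported over 12 and 24 months, with no stated cap.

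**Collection of relapse counts.** Protocol 9.1.1 collects counts at Months 12 and 24 only. SAP Section 6 moves all Year 2 visits by the length of the Year 2 delay; Protocol 9.2.4 says their timing may need adjusting. Under SAP 14.1.1, if the lead question is not answered at Visit 6, the second-year count is missing.

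**Calendar.** The Protocol milestones give "Last Patient First Visit (last patient to sign ICF): 28-Nov-2022", "Last Patient Last Visit: 03-Jan-2025" and "Database Lock: 17-Feb-2025".

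**Wording on Month 30.** Protocol 9.7 and the abstract say the final safety assessment *would* occur then if Year 2 is delayed. The footnotes to Protocol 9.1.1 and Table 1 say the final visit *may* occur then.

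**The concern.** The stated objective is relapse over 24 months. If the window depends on whether Year 2 was delayed, patients with delayed recovery of lymphocytes are observed for longer than the rest under the same label. A rate allows for this through its denominator. A cumulative proportion does not: more time gives more patients with at least one relapse.

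The second strand runs the other way. When Visit 6 moves with the Year 2 course, a patient who entered late may still be waiting for it when the study closes. The SAP's missing-data rule depends on the Visit 6 answer, not on time observed, so a patient with more than 24 months of follow-up could have no usable second-year count. Such losses would be tied to delay and to late entry, so they are not obviously random. They could also blur the planned comparison of completers with drop-outs, because the reasons listed for the group "Patients not completing the 24-month study (i.e., lost to follow-up, withdrawing consent, protocol deviations" do not include study closure.

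**Working it through.** **Inputs.** Last consent 28-Nov-2022, first consent 31-Jul-2019 and last visit 03-Jan-2025 (Protocol milestones); consent up to 60 days before baseline (Protocol Table 1); 30.4375 days per month and 365.25 per year (SAP Section 9). The relapse rates, the share of patients delayed and the length of delay are not in the documents and are assumed below.

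**1. The plan's own figures.** 24 + 6 = 30 months. The sensitivity bound is 2 × 365.25 + 1 = 731.5 days, so the SAP already has a 24-month cap, but it applies it only to the sensitivity ARRs.

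**2. Effect of the longer window on a proportion.** With a constant rate r per year, the chance of at least one relapse in t years is 1 − exp(−r·t). The pooled increase is the share followed to 30 months times the difference.

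| Assumed rate per year | 24 months | 30 months | Difference (points) | Pooled, 10% delayed | Pooled, 30% delayed |
|---|---|---|---|---|---|
| 0.05 | 9.5% | 11.8% | 2.2 | 0.2 | 0.7 |
| 0.1 | 18.1% | 22.1% | 4.0 | 0.4 | 1.2 |
| 0.2 | 33.0% | 39.3% | 6.4 | 0.6 | 1.9 |
| 0.3 | 45.1% | 52.8% | 7.6 | 0.8 | 2.3 |

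These figures let every delayed patient run the full 30 months. With a 2-month delay at 0.2 per year, the proportion is 1 − exp(−0.2 × 26/12) = 35.2%. That is 2.2 points above 33.0%, or 0.2 to 0.7 points pooled at 10% to 30% delayed.

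**3. Effect on the ARR.** With a constant rate, expected relapses are r·t and time on study is t, so the ratio is r whether t is 24 or 30 months. The mean ARR shifts only if the rate changes over time.

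**4. Calendar room.** 28-Nov-2022 to 03-Jan-2025 is 767 days, and 767/30.4375 = 25.2 months. If dosed on the day of consent, the last patient can absorb 25.2 − 24 = 1.2 months of delay. With the full 60 days, 767 − 60 = 707 days remain, or 23.2 months, and Month 24 falls on 26-Jan-2025, 23 days after the last visit.

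Month 30 is 30 × 30.4375 = 913 days after first dose. Counting back from 03-Jan-2025 gives a latest first dose of about 5 July 2022. From then to the last consent is 146 of the 1,216 days of enrollment, or 12% of the calendar; the documents do not give the share of patients.

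**5. What the missing-data rule would do.** Take a constructed patient first dosed on 1 December 2022 with a 4-month delay. At closure 764 days have passed, or 25.1 months. Visit 6 is due at Month 28, about 1 April 2025. Without a Visit 6 answer the second-year count is missing (SAP 14.1.1), so the Month 24 ARR is missing (SAP 14.1.4). The sensitivity ARR keeps the first year but bounds time at 366.25 days, so it leaves out the second year that was observed.

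**The case against.** The strongest reply is that the 24-or-30-month window is stated openly, so it is a choice and not a slip. A cap also changes what is estimated: a patient delayed by 6 months would contribute only about 6 months after the second course. This stands as a reason to show both periods. It does not justify giving proportions over unequal windows a 24-month label.

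Missing relapse data are also partly provided for. A Table 1 footnote has relapses recorded continuously, the sensitivity ARR retains first-year data, and SAP 14.1.4 considers multiple imputation above 5% missing. None of these lets an observed second year count when the Visit 6 answer is absent.

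A reader might infer four stronger things that the documents do not support:

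- *That Month 30 follow-up is guaranteed and then cut off.* Protocol 9.2.3 lets the end of data collection stop follow-up, and most of the wording is permissive. Only the safety sentence says *would*.
- *That the SAP cutoff falls after database lock.* SAP 6.5 says "The corresponding cutoff is expected by the end of March 2025"; that is an outer bound, which a lock on 17-Feb-2025 satisfies.
- *That these patients must be non-completers.* Neither SAP 8.2 nor SAP 10.1 ties completion to attending Visit 6, and SAP 10.1 tabulates discontinuation reasons without a closed list.
- *That late, delayed patients are known to exist.* No document says so. The amendment that set the closing date is dated September 2024. On the latest first dose (27-Jan-2023), a 6-month delay would put the second course at about July 2024, so any delay could already be seen.

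**Conclusion.** The point holds in two parts of different weight.

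The main part is certain from the text. The 24-month relapse outcomes have a window of 24 months for most patients and up to 30 for those with a delayed Year 2. The harm falls on the three relapse proportions in SAP 14.2. The central illustration is 0.6 to 1.9 percentage points at 0.2 relapses per year. It assumes a constant rate, 10% to 30% of patients delayed and the full 6-month delay. Over assumed rates of 0.05 to 0.3 the range is 0.2 to 2.3 points, and shorter delays give less. Under a constant rate the primary ARR is little affected.

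The second part is conditional. If any patient first dosed after about 5 July 2022 had a delay long enough to push Visit 6 past 03-Jan-2025, the SAP's rule could discard relapse information from a completed 24 months. The 25.2-month figure is firm; the number of such patients is unknown. The Month 24 shortfall of 23 days needs the full 60-day window for the last patient and is minor.

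**What to change.** 1. In SAP 14.1.1 and 14.2, evaluate the 24-month relapse outcomes, above all the three proportions, on days 1 to 731 from first dose whatever the Year 2 delay. Use relapse onset date for the count and the matching time at risk. Report months 25 to 30 separately.
2. State that a patient whose Visit 6 would fall after closure has the Visit 6 relapse question taken at the last contact by the closing date. If sites have already closed, the continuous relapse record in Table 1 is the natural source. In SAP 8.2 and 10.1, count patients with 24 months from first dose as 24-month completers, and list study closure as its own disposition reason.
3. Reconcile the *would* wording on Month 30 in the Protocol abstract and 9.7 with the *may* wording in the footnotes and the end-of-data-collection limit in 9.2.3.

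The cost is SAP wording, one protocol clarification and one disposition category. The cap is one the SAP already uses. The downside is that relapses after Month 24 in delayed patients leave the main 24-month results and move to a supplementary line.

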9.2.4 Frequency of Assessments

Table 1 lists the Schedule of Assessments. Patients are considered enrolled once the informed consent form (ICF) has been signed prior to any data collection for this study. The Baseline Visit is the visit immediately prior to the patient initiating treatment with cladribine tablets. If the sites anticipate a delay between the decision to start cladribine tablets and patient access to cladribine

tablets (i.e. due to delays in cladribine tablets availability or access), the site can perform a Screening Visit first to determine eligibility of the patient and a subsequent Baseline Visit closer to the time the patient starts taking cladribine tablets. Data entered during the Baseline Visit are considered baseline data for the purposes of analysis.

Sites are asked to enter patient follow-up data for up to 24 months after a patient received the initial month dose of cladribine tablets if Year 2 treatment course is not delayed, and up to 30 months after initial dose if Year-2 treatment course is delayed up to 6 months. Visits will be conducted within the context of routine clinical care; thus, the timing of study visits is approximate and not mandated by the study protocol.

It is anticipated that patients enrolled in the study may not immediately start cladribine tablets after the decision to initiate cladribine tablets is made, owing to the need to first discontinue their current oral or infusion DMD (for a time period determined by the investigator) and to potential delays in obtaining cladribine tablets in the clinical setting. The initial PRO only collection (Month 1) is intended to be obtained after the patient has started treatment with cladribine tablets. The timing of Visit 1 (Month 2) and the subsequent visits may need to be adjusted based upon the actual start date of cladribine tablets, which will be recorded by the investigator.

In accordance with the USPI, it is anticipated that patients may not receive their second course of cladribine tablets precisely 12 months after the initiation of cladribine tablets owing to ALC levels <800 cells per microliter or other potential clinical factors. In the event that the second course of cladribine tablets is delayed beyond Month 13, the PRO only collection scheduled for Month 13 should be adjusted to occur during the start of the second course of cladribine tablets. The timing of Visit 4 (Month 14) and the subsequent visits may need to be adjusted based upon the actual start date of the second course of cladribine tablets, which will be recorded by the investigator.

Table 1. Schedule of Assessments

Assessments	Data collection time points (as expected based on routine clinical practice)									
	Pre-baseline Screening Visit	Baseline Visit ^a	PRO Only ^b	Visit #1	Visit #2	Visit #3	PRO Only ^b	Visit #4	Visit #5	Visit #6
(Days -60 to 0)	Month 0	Month 1	Month 2	Month 6	Month 12	Month 13	Month 14	Month 18	Month 24 ^j	
Informed consent	X									
Medical history, previous relapses, previous DMD treatment		X								
Inclusion / exclusion criteria	X									
Demographic data	X									
Pregnancy test, HIV, hepatitis B and hepatitis C and tuberculosis status		X				X				
Cladribine tablets ^c		X		X		X		X		
Other MS DMD during study period, if applicable				X		X		X		X
Neurological examination as per standard of care		X			X	X			X	X
Physical examination as per standard of care		X								
Relapse count (prospective) ^d						X				X
MRI documentation ^e		X			X	X			X	X
Hematology assessment (ALC, CBC, lymphocyte subsets, immunoglobulins) ^f		X		X	X	X		X	X	X
Patient-reported outcomes										
Treatment adherence ^g		X ^h	X	X			X	X		
TSQM		X ^h			X	X				X
SF-36		X ^h			X	X				X

Company substance code: 700568
Protocol number: MS700568_0079

^a Duration between end of previous treatment and start of cladribine tablets is at the discretion of the investigator.

^b At the PRO only time point, patients fill out the PROs at their home; patients do not come to the clinic for filling out PROs at these time points.

^c Cladribine tablets are expected to be taken according to the USPI. If cladribine tablets are discontinued, reasons for discontinuation and follow-up MS treatment will be collected.

^d Relapse count includes relapses associated with hospitalization and/or glucocorticoid use.

^e For baseline MRI documentation sites are asked to record patients' most recent MRI results prior to starting cladribine tablets, which is expected to have been taken within the prior 90 days. During follow-up, MRI scans are provided as available per routine practice. MRI documentation collected at baseline and follow-up are assessed by a central neuroradiology center. Specific instructions for transfer of the MRIs to the central neuroradiology center will be provided in a separate manual.

^f Investigators are expected to assess patients' ALC in accordance with the USPI, that is, before initiating cladribine tablets in Year 1, before initiating cladribine tablets in Year 2, and 2 and 6 months after start of treatment in each treatment year or as clinically indicated. It is assumed that investigators will not exclusively assess the ALC, but rather the CBC and, at some of these time points, also lymphocyte subsets. These data will be reported as available from routine practice. If the investigator assesses **CC1** [REDACTED], these data should be recorded as well.

^g Treatment adherence questions, based on modified versions of the MS-TAQ, will be completed by patients via ePRO: at Baseline Visit (modified for once or twice daily oral dosing to assess adherence during last previous oral DMD treatment or modified for infusion dosing to assess adherence during last infusion DMD treatment) as well as at the end of Month 1, Month 2, Month 13, and Month 14 (modified for cladribine tablets).

^h Baseline PRO scales will be completed before first cladribine tablet dose is taken.

ⁱ Adverse events CCI [REDACTED], relapse count, PDDS score and MRI data will be collected as per running page and will be recorded on an ongoing basis as new information is collected for up to 24 months (or 30 months if treatment is delayed).

^j If Year 2 treatment is delayed, final follow-up visit may occur at Month 30.

Abbreviations: ALC=absolute lymphocyte count, BDI-FS=Beck-Depression Inventory-Fast Screen, CBC=complete blood count, DMD=disease-modifying drug, ePRO = electronic Patient-Reported Outcome, HIV=human immunodeficiency virus, **CCI** [REDACTED], MFIS-5=Modified Fatigue Impact Scale – 5-item version, MRI=magnetic resonance imaging, MS=multiple sclerosis, MS-TAQ=Multiple Sclerosis Treatment Adherence Questionnaire, PDDS=Patient Determined Disease Steps, PRO=Patient-Reported Outcome, SF-36=36-Item Short Form Health Survey; TSQM=14-Item Treatment Satisfaction Questionnaire for Medication, USPI=US Prescribing Information; WPAI-MS=Work Productivity Activity Impairment – MS.

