### **Time Window**

Day 1 is the day of the start of the study dose; the day before is Day -1 (Day 0 is not defined).

Study day / Study dose day is defined relative to Day 1.

Visits will be conducted within the context of routine clinical care; thus, the timing of study visits is approximate and not mandated by the study protocol. The PDSS and MS-TAQ will be analyzed according to the visit collected through the eCRF. For all the other PROs collected at Months 6, 12, and 24, the analysis windows are  $\pm$  1 month (30 days). The analysis windows for the different months will be derived considering Day 1 (day of start of study dose), regardless of possible treatment delays in the second year. Endpoints without an analysis window will be analyzed according to the visit collected through the eCRF (if available).

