2.) During the last 4 weeks (28 days) that you were taking this medication, how many days were you supposed to take this medication? (Check one)

Twice a day (58 times)	
Once a day (28 times)	
Other, please specify:	

3.) Did you miss or forget to take any doses of this medication during the last 4 weeks (28 days) that you were taking the medication? (Check one)

Yes	
No	

4.) How many doses did you miss or forget to take? (Complete blank)

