**IF YOU HAVEN'T SKIPPED ANY DOSES, SKIP TO QUESTION 6**

**(Complete #5 only if you missed a dose)**

5.) How important were the following factors in missing or forgetting to take a dose? (Please check one answer for each)

	Not important at all	A little important	Moderately important	Extremely important
Memory problems	0	1	2	3
Too busy	0	1	2	3
Side effects of medication	0	1	2	3

	Not important at all	A little important	Moderately important	Extremely important
Needing someone to help me take my medication	0	1	2	3
Ran out of medication or could not refill my prescription	0	1	2	3
Away from home and could not access my medication	0	1	2	3
Feeling anxious, depressed, or nervous about taking my medication	0	1	2	3
Dissatisfaction with my medication	0	1	2	3
Did not want taking my medication to interfere with activities	0	1	2	3
Tired of taking my medication	0	1	2	3
Did not feel like taking my medication	0	1	2	3

6.) Overall, how hard or easy do you feel it is to take your current infused/intravenous (IV) Multiple Sclerosis treatment as recommended by your physician? (Check one)

Extremely easy	1
A little hard	2
Moderately hard	3
Very hard	4
Extremely hard	5

7.) Overall, how satisfied are you with how things have been with your treatment during the past 4 weeks (28 days)? (Check one)

Not satisfied at all	1
A little satisfied	2
Moderately satisfied	3
Very satisfied	4
Completely satisfied	5

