**MS-TAQ modified for cladribine tablets**

1.) What treatment week of cladribine tablets did you most recently complete? (check one)

Year 1, Treatment Week 1	
Year 1, Treatment Week 2	
Year 2, Treatment Week 1	
Year 2, Treatment Week 2	
Other, please specify:	

2.) How many cladribine tablets were you supposed to take during this treatment week?  
(complete the blank)

3.) Did you miss or forget to take any cladribine tablets during this treatment week?  
(Check one)

Yes	
No	

4.) How many cladribine tablets did you miss or forget to take? (Complete blank)

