**IF YOU HAVEN'T SKIPPED ANY DOSES IN THE PAST 28 DAYS, SKIP TO QUESTION 6**

**(Complete this section only if you missed a dose in the past 28 days)**

5.) How important were the following factors in missing or forgetting to take a dose? (Please check one answer for each)

	Not important at all	A little important	Moderately important	Extremely important
Memory problems	0	1	2	3
Too busy	0	1	2	3
Side effects of medication	0	1	2	3
Ran out of medication or could not refill my prescription	0	1	2	3
Away from home and could not access my medication	0	1	2	3

	Not important at all	A little important	Moderately important	Extremely important
Feeling anxious, depressed, or nervous about taking my medication	0	1	2	3
Dissatisfaction with my medication	0	1	2	3
Did not want taking my medication to interfere with activities	0	1	2	3
Tired of taking my medication	0	1	2	3
Did not feel like taking my medication	0	1	2	3

[figure not shown]
[figure not shown]
[figure not shown]
6.) Overall, how hard or easy do you feel it is to take cladribine tablets as recommended by your physician during your treatment week? (Check one)

Extremely easy	1
A little hard	2
Moderately hard	3
Very hard	4
Extremely hard	5

7.) Overall, how satisfied are you with how things have been with your cladribine tablet treatment during your treatment week? (Check one)

Not satisfied at all	1
A little satisfied	2
Moderately satisfied	3
Very satisfied	4
Completely satisfied	5

CCI

---

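### When the second course is delayed, the Month 13 cladribine adherence form can describe a Year 1 treatment week, and the 28-day routing can suppress reasons for missed doses

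*Protocol*

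**What the plan says.** **Timing.** Footnote g to Table 1 (Protocol 9.2.4) has patients complete the cladribine version of the MS-TAQ "at the end of Month 1, Month 2, Month 13, and Month 14 (modified for cladribine tablets". The text of 9.2.4 makes an exception when the second course starts later than Month 13: "the PRO only collection scheduled for Month 13 should be adjusted to occur during the start of the second course of cladribine tablets". It adds that the Month 14 visit may be re-timed to the actual start of that course.

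**What the form asks.** Item 1 of the cladribine version (SAP 18) reads "What treatment week of cladribine tablets did you most recently complete". Items 2 to 4 then ask about the tablets due and missed in that treatment week. Item 5, which rates the reasons for missing doses, carries a different condition: "Complete this section only if you missed a dose in the past 28 days". The oral baseline version carries the same 28-day condition, although its item 3 concerns the last 28 days on the drug. The infusion version says only "Complete #5 only if you missed a dose".

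**Analysis.** SAP 9 (Time Window) states: "The PDSS and MS-TAQ will be analyzed according to the visit collected through the eCRF". SAP 16.4 summarises the questions one by one, without imputation. Protocol 9.7.3 promises a description of adherence for the first and for the second course.

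**The concern.** Adherence is a secondary objective, and SAP 16.4 gives the questionnaire two purposes: to measure adherence and to identify barriers to it. Each can be damaged by a mismatch of reference periods.

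- **Wrong week.** A form filled in at the very start of a delayed second course precedes completion of Year 2 Week 1. The most recently completed week is then in Year 1, but the record carries the Month 13 label and no SAP rule moves it. A first-course answer can appear in the second-course summary.
- **Lost reasons.** A patient can report missed tablets in item 3 and then, following the printed routing, be told to skip item 5 because those doses lie more than 28 days back. The SAP sets no denominator for item 5 and no check against item 3, so a misrouted patient looks the same as one who missed nothing.

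**Working it through.** The documents give no figure to reproduce, so this is a count of days.

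**Inputs**
- One month = 30.4375 days (SAP 9, Conversion Factors).
- Each treatment week has 4 or 5 dosing days, at the start of the first and of the second month of each treatment year (Protocol 9.2.2).
- The form is due at the end of Months 1, 2, 13 and 14 (footnote g).
- The second course may be delayed by at most 6 months (Protocol 9.2.2; SAP 6).
- Assumption: a 28-day look-back from day d runs from d − 27 to d if the completion day counts, or from d − 28 to d − 1 if it does not. Both are shown.

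**1. Delayed patients answering as the second course starts.** Year 1 Week 2 starts on day 31; a five-day week ends on day 35.
- Start just after Month 13: 13 × 30.4375 = 395.7, so day 397. Gap: 397 − 35 = 362 days; 362 / 30.4375 = 11.9 months.
- Start just after Month 18 (12 + 6): 18 × 30.4375 = 547.9, so day 549. Gap: 549 − 35 = 514 days; 514 / 30.4375 = 16.9 months.

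The 28-day look-back contains no day of that earlier week, so item 5 would be skipped for it as well.

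**2. On-schedule patients, form completed exactly at month end.** Ranges run from counting the completion day to not counting it.

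| Form | First dosing day | Completion day | Covered, 5-day week | Covered, 4-day week |
|---|---|---|---|---|
| Month 1 | 1 | 30 | 3 to 4 | 2 to 3 |
| Month 2 | 31 | 61 | 2 to 3 | 1 to 2 |
| Month 13 | 366 | 396 | 2 to 3 | 1 to 2 |
| Month 14 | 397 | 426 | 3 to 4 | 2 to 3 |

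The look-back therefore loses the first 1 to 3 dosing days but not the whole week.

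**3. Early or late completion (Month 1, five-day week).** Two or more days early, all five dosing days are covered. Three days late (day 33), the look-back starts on day 6 or day 5 and holds 0 or 1 dosing day. Five days late, it holds none on either count. Protocol 9.2.4 calls visit timing approximate, so delays of this size are foreseeable.

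**4. Oral baseline form.** If a patient stopped the drug w days before answering, the look-back holds about 28 − w days on the drug, and none once w reaches 28. The documents leave w to the investigator. The form also prints "Twice a day (58 times" for 28 days of twice-daily dosing; 2 × 28 = 56. Its item 1 lists three drugs with no free-text choice, while Protocol 7.3 names eight oral drugs besides cladribine, so five cannot be selected.

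**5. What can still be changed.** Last consent was 28-Nov-2022. Adding the 60-day screening window gives 27-Jan-2023; adding 14 months and a 6-month delay gives about 27-Sep-2024. That is before protocol version 11 (21-Oct-2024) and SAP 4.0 (23-Jan-2025).

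**The case against.** The strongest reply has five parts.

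- **The timing phrase has another reading.** A course spans two treatment weeks in successive months, so its start could mean its first month, and other passages put the form at the end of Month 13. This stands as far as it goes: the text permits the error and does not force it. Wording that allows either reading still needs an analysis rule.
- **Visits move with the delay and item 1 names the week.** SAP 6 shifts all Year 2 visits, item 1 has a free-text option, and the SAP tabulates single items, so a form about an earlier week is visible. True, but visible is not reassigned: nothing in the SAP stops the remaining items of that form from being summarised under Month 13.
- **The printed form may not be the programmed one.** The ePRO branching is not in the documents. This stands, and it is why the routing effect is a possibility and not an established loss.
- **The baseline points lose little.** All prior disease-modifying drugs are in the eCRF, no analysis is stated to use 58, and the infusion form's different wording fits its one-year reference period. Accepted.
- **Tablet counts are recorded separately** (SAP 13). They give an independent compliance measure, but not patient-rated reasons, and SAP 13 itself says that the adherence endpoint is assessed by questionnaire.

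A reader might also infer that missed-tablet counts are wrong throughout. The documents do not support that: items 3 and 4 refer to the treatment week, and the 28-day condition governs item 5 only.

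**Conclusion.** Two conflicts in the text are real, and either can distort a descriptive secondary result. Where the second course is delayed beyond Month 13, a form answered before Year 2 Week 1 ends describes a week about 12 to 17 months old and can be reported as second-course adherence. In the cladribine and oral forms, patients who report a missed dose can be routed past the reasons. In the cladribine form the look-back covers only part of the week when the form is on time, and none of it when the form is about 3 to 5 or more days late.

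Several wider inferences are not supported. Year 2 adherence as a whole is not lost, because Week 2 can still be captured at the re-timed Month 14 visit. The number affected cannot be estimated: the 20% to 25% with Grade 3 or worse lymphopenia in Protocol 7.4 is not a rate of delayed second courses. A bias of the reasons towards early responders is plausible but not shown. The primary annualized relapse rate is unaffected.

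The sizes assume dosing from the first day of each treatment month and routing as printed.

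**What to change.** In SAP 9 and 16.4, before the analysis is run:

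1. Assign each cladribine MS-TAQ record to a treatment week by its item 1 answer, checked against the exposure log, and not by the eCRF visit label alone. Do not count a form that refers to a Year 1 week as Month 13.
2. Summarise item 5 among patients who answered yes to item 3, with the number missing shown, and state that the 28-day routing may have suppressed answers.
3. If the oral twice-daily denominator is used, compute it as 56. Take the prior drug from the eCRF log.

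For the record, reconcile the text of Protocol 9.2.4 with footnote g, and the item 5 routing with item 3 in the cladribine and oral forms. These edits cannot recover forms already collected.

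The cost is a few lines in the SAP and some programming, with no new data. The protocol plans database lock for 17-Feb-2025. The downside is that some records will move to another treatment week or be shown as missing.
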